## 4 GENERAL CONSIDERATIONS FOR DATA ANALYSIS

### 4.1 REPORTING CONVENTIONS

The summary tables, figures, and by-subject listings will be prepared using the following conventions:

- Unless otherwise specified, the baseline value is defined as the last non-missing assessment prior to the first dose of study treatment. The last non-missing evaluation includes unscheduled and repeat visits.
- If the date of interest occurs on or after the first dose/randomization date, the study day will be calculated as “date of interest – date of first dose/randomization + 1”.
- If the date of interest occurred prior to the first dose/randomization date, then study day will be calculated as “date of interest – date of first dose/randomization”.
- Both safety and efficacy analysis results will be presented using descriptive statistics. Depending on the parameter, the difference from baseline will either be computed using the original scale (raw change from baseline) or on the log scale and back transformed for reporting.
- Categorical data will be summarized by treatment group in terms of frequency counts and percentages.
- Continuous variables will be summarized by treatment group using descriptive statistics (the number of subjects [n], mean, median, SD, minimum, and maximum) of the values at each visit and the change from baseline to each visit. PK parameters and other laboratory analytes that are believed to follow an

approximate log-normal distribution will also be summarized by the geometric mean and coefficient of variation (expressed as a percent).

- CIs will be presented as 2-sided 95% CIs.
- All mean, median, and CI values will be formatted to one more decimal place than the measured values. SD values will be formatted to two more decimal places than the measured value. Minimum and maximum will be formatted to the same number of decimal places as the measured value. The maximum number of decimal places reported shall be four for any summary statistic.
- All percentages will be rounded to one decimal place. The number and percentage of responses will be presented in the form XX (XX.X), where the percentage is in the parentheses.
- Change from baseline is calculated as a post-baseline value minus the baseline value.
- All laboratory data will be reported using standard international units.
- All analyses and summary tables will include the analysis set sample size (i.e., number of subjects) in the column headings.

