- Listing will include both the randomized treatment and actual treatment, if different.
- By-subject listings will be presented for all subjects in the relevant analysis sets, and sorted by treatment allocation, study site (if applicable), subject ID, date, and visit. Numeric data will be listed to the same number of decimal places as recorded on the electronic case report form (eCRF) or other data source. Data collected on log forms, such as adverse events (AEs), will be presented in chronological order within the subject.
- SAS® Software Version 9.4M5 (SAS Institute Inc., Cary, NC, USA.) is to be used for all analyses including tables, listings, and figures.
- Partial dates will be imputed as follows:
  - If day and month is missing but year is present, the 1st of July of the noted year will be used.
  - If day is missing but year and month are present, the 15th of the noted month and year will be used.
- Non-PK lab data that are continuous in nature but are less than the lower limit of quantitation (LOQ) or above the upper LOQ will be imputed as follows:
  - A value that is 1/10th unit less than the lower LOQ will be used for calculation of descriptive statistics if the datum is reported in the form of “ $< x$ ” (where x is considered the lower LOQ). For example, if the values are reported as  $< 50$  and  $< 5.0$ , values of 49 and 4.9, respectively, will be used for calculation of summary statistics. An exception to this rule is any value reported as  $< 1$  or  $< 0.1$ , etc. For these, a value of 0.9 or 0.09, respectively, will be used for calculation of summary statistics.
  - A value that is 1/10th unit above the upper LOQ will be used for calculation of descriptive statistics if the datum is reported in the form of “ $> x$ ” (where x is considered the upper LOQ). Values with decimal points will follow the same logic as above. The LOQ will be used for calculation of descriptive statistics if the datum is reported in the form of “ $\leq x$ ” or “ $\geq x$ ” (where x is considered the LOQ).
- PT101 plasma concentration values that are equal to or below the LOQ will be interpolated to 50% of the lower LOQ for the analytical assay throughout the dataset.

- Medical Dictionary for Regulatory Activities (MedDRA) version 24.0 or newest will be used to code AEs and medical history, World Health Organization drug dictionary (WHODD) version Sep 2021 or newest will be used for medication coding.

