## 7 PHARMACOKINETIC AND PHARMACODYNAMIC ANALYSES

### 7.1 PHARMACOKINETIC ASSESSMENTS

Blood samples for PK assessment will be collected as outlined in the protocol and outlined in [Appendix A](#). The PK endpoints will include change in serum concentration of PT101 over time and analysis of PK parameters. PK parameters for PT101 will be estimated using noncompartmental analysis (NCA) methods. PK parameters that will be assessed are shown in [Table 7](#). The maximum concentration ( $C_{max}$ ) for each subject will be determined along with the actual time it occurs ( $T_{max}$ ). As there are multiple doses given prior to complete elimination, the terminal elimination constant ( $K_{el}$ ) will be estimated from the concentrations observed following the final concentration peak. If there exists at least one observed concentration following the final peak, log-linear regression will be used to estimate the slope of the

concentration-time curve, the absolute value of which will be the  $K_{el}$ . From this, the terminal elimination half-life ( $t_{1/2}$ ) will be estimated using the formula:

$$t_{1/2} = \ln 2 / K_{el}.$$

The area under the concentration-time curve (AUC) from zero to infinity will be estimated in two parts: (1) AUC from zero to last observed concentration; and (2) AUC from last observed to infinity.

$$AUC_{0-\infty} = AUC_{0-t_{last}} + AUC_{t_{last}-\infty}.$$

The portion of the AUC up to the last observed concentration will be estimated using the log-linear trapezoidal method. The incremental portions of the AUC between each observed concentration will be estimated individually and summed to give the AUC across the period. The absorption phase will use a linear interpolation.

$$AUC_i = \frac{1}{2}(C_1 + C_2)(t_2 - t_1).$$

While the elimination phase will use a logarithmic interpolation, following the equation below.

$$AUC_i = \frac{C_1 - C_2}{\ln C_1 - \ln C_2} (t_2 - t_1).$$

The portion of the AUC following the last observed concentration will be assumed to follow an exponential elimination dictated by the terminal elimination constant. It will be estimated as follows:

$$AUC_{t_{last}-\infty} = \int_{t_{last}}^{\infty} C_{last} \cdot e^{-K_{el} \cdot t} dt = \frac{C_{last}}{K_{el}}.$$

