**Table 7. Standard Pharmacokinetics Parameters**

Name	Description
$C_{max}$	Maximum concentration in a dosing interval
$C_{min}$	Minimum concentration in a dosing interval
$T_{max}$	Time of occurrence of $C_{max}$ within a dosing interval
$t_{1/2}$	Terminal elimination half-life
$AUC_{0-t}$	Area under the concentration-time curve from time 0 to the last measurable concentration in a dosing interval
$AUC_{0-\infty}$	Area under the concentration-time curve from time 0 extrapolated to infinity
$CL/F$	Apparent total body clearance following administration
$V_d/F$	Apparent volume of distribution following administration

Serum concentrations of PT101 will be listed and summarized by treatment group using descriptive statistics. PK parameters will be calculated using the actual time of sample collection whereas nominal time will be used for graphical presentations. Summary statistics including arithmetic mean, geometric mean, % coefficient of variation, SD, median, minimum, and maximum of the PK parameters listed in [Table 7](#) will

be summarized. All individual PK parameters will be listed in a by-subject listing. PK parameters will be analyzed for the PK & Biomarker analysis set.

Graphical presentations will use the nominal time of sample collection. Mean and median concentration time profiles will be calculated by dose-level (cohort) and nominal time and plotted on linear and semi-log transformed scales. The mean profiles will include SD error bars to indicate precision in the observed mean concentration; median profiles will include the minimum and maximum observed values. Individual and mean PT101 concentration time profiles will also be produced on linear and semi-log transformed scales for each cohort at CCI. Mean and median trough concentration time profiles will be calculated by cohort and nominal time and plotted on linear and semi-log transformed scales. Individual and mean trough concentration time profiles will be plotted on linear and semi-log transformed scales for each cohort.

Dose-proportionality of CCI will be assessed using a linear regression fit of  $\ln(AUC/C_{max})$  versus  $\ln(\text{Dose})$  to estimate slope and confidence interval of slope. Natural log-transformed exposures versus natural log-transformed dose relationship for both  $AUC_{0-\infty}$  and  $C_{max}$  will also be presented.

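### SAP 7.1 allows Kel to be fitted with a single post-peak concentration, which cannot give a slope, and no sentence keeps LLOQ/2 values out of that fit

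*SAP*

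**What the plan says.** **Kel rule (SAP 7.1).** Kel "will be estimated from the concentrations observed following the final concentration peak". The condition for running the fit is: "If there exists at least one observed concentration following the final peak, log-linear regression will be used". Kel then gives t1/2 = ln2/Kel and the extrapolated tail of AUC0-inf as Clast/Kel. Table 7 lists t1/2, AUC0-inf, CL/F and Vd/F among the reported parameters. The section gives no larger minimum, no fit criterion and no rule for profiles that cannot support a slope. It does not say whether the peak itself may be used.

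**Rule for low values (SAP 4.1).** The rule covers "PT101 plasma concentration values that are equal to or below the LOQ". The instruction for this group is that they "will be interpolated to 50% of the lower LOQ for the analytical assay throughout the dataset". The neighbouring rule for non-PK laboratory data is narrower: "A value that is 1/10th unit less than the lower LOQ will be used for calculation of descriptive statistics". Section 4.1 opens with: "The summary tables, figures, and by-subject listings will be prepared using the following conventions".

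**Which data enter the PK parameters (SAP 7.1, text under Table 7).** "PK parameters will be calculated using the actual time of sample collection whereas nominal time will be used for graphical presentations". This settles which times are used but not which concentrations. Table 7 ends AUC0-t at the last measurable concentration. The same text refers to serum ("Serum concentrations of PT101 will be listed and summarized by treatment group"), whereas 4.1 refers to plasma.

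The protocol makes PK parameters a secondary endpoint (2.2.2). Its PK analysis section (9.3.6.1) has no rule for values below the LOQ.

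**The concern.** There are two gaps, and the first does not depend on the second.

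1. A regression slope needs at least two points at different times. A rule that starts the regression at one post-peak point fails when followed literally. If the analyst rescues it by adding the peak, the line passes exactly through two points and nothing shows whether the terminal phase was reached.
2. The LLOQ/2 rule covers the whole dataset and lacks the descriptive-statistics limit of the rule beside it. A programmer who builds one PK dataset under 4.1 could pass imputed values to the noncompartmental analysis. Another who reads *observed* in 7.1 as quantifiable would not. Both could claim to follow the SAP and report different half-lives.

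At stake are t1/2 and whatever is derived from Kel: AUC0-inf through its tail, and CL/F and Vd/F.

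**Working it through.** The documents state no half-life, LLOQ or Kel, so there is no figure of the plan's own to reproduce.

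**Step 1: the minimum.** The model ln C = a − Kel·t has two unknowns. One point gives a design matrix of rank 1, and 2 is needed. With the peak added there are two points and two parameters, so residual degrees of freedom = 2 − 2 = 0.

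**Step 2: does imputation matter if it enters the fit?** Everything here is assumed: one-compartment SC profile, absorption half-life 1 d, no error, sparse sampling on days 1, 3, 7, 14, 21 and 28. With true half-life T, C(t) is proportional to 2^(−t/T) − 2^(−t), scaled so that the sampled peak (day 3) is M times the LLOQ. Only post-peak points are fitted, as 7.1 words it:

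Kel = −Σ(t − t̄)·ln C / Σ(t − t̄)²

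For days 7, 14, 21 and 28, t̄ = 17.5 and Σ(t − t̄)² = 2 × (10.5² + 3.5²) = 245.

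Worked case, T = 2 d, M = 50:
- Day 3: 2^(−1.5) − 2^(−3) = 0.2286. Day 7: 2^(−3.5) − 2^(−7) = 0.0806, so C = 50 × 0.0806/0.2286 = 17.63 × LLOQ. Days 14, 21 and 28 give 1.70, 0.15 and 0.01.
- With LLOQ/2: ln C = 2.869, 0.528, −0.693, −0.693. Σ(t − t̄)·ln C = −30.13 − 1.85 − 2.43 − 7.28 = −41.68. Kel = 41.68/245 = 0.170, so t1/2 = 4.1 d.
- Low values excluded: Kel = (2.869 − 0.528)/7 = 0.334, so t1/2 = 2.1 d.

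The same calculation for other sparse-schedule cases:

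| True t1/2, peak/LLOQ | Days 7, 14, 21, 28 (× LLOQ) | With LLOQ/2 | Excluded |
|---|---|---|---|
| 2 d, 50 | 17.63, 1.70, 0.15, 0.01 | 4.1 d | 2.1 d |
| 3 d, 20 | 10.17, 2.10, 0.42, 0.08 | 4.6 d | 3.1 d |
| 5 d, 20 | 13.88, 5.37, 2.04, 0.77 | 4.4 d | 5.05 d |
| 2 d, 20 | 7.05, 0.68, 0.06, 0.005 | 6.1 d | no slope |

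The last row joins both gaps. Exactly one quantifiable point follows the peak, so the condition in 7.1 is met. Without imputation there is no slope; with it, ln C = 1.953 and three times −0.693, Kel = 27.78/245 = 0.113 and t1/2 = 6.1 d.

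**Step 3: denser assumed schedules at M = 20 and 50.** B samples days 1, 3, 5, 7, 10 and 14. C samples days 1 and 3, then one to six half-lives after day 3. With three half-lives and two peaks each, there are 12 cases. Seven have no post-peak value at or below the LLOQ and do not change. Two of the other five:
- B, T = 2 d, M = 20: days 5, 7 and 10 give 12.74, 7.05 and 2.65, and day 14 gives 0.68, set to 0.5. Kel = 16.58/46 = 0.360, so t1/2 = 1.92 d. Excluded: 3.99/12.67 = 0.315, so 2.20 d. Here imputation lands nearer the true 2 d.
- C, T = 5 d, M = 50: only the last value (0.96) is imputed. Kel = 68.7/437.5 = 0.157, so 4.4 d versus 5.0 d excluded. This is the largest shift among the dense cases, and it moves away from the truth.

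The remaining three (C at M = 20) give 1.96 versus 2.18 d, 2.97 versus 3.09 d and 5.01 versus 5.03 d, each slightly nearer the truth with imputation. The excluded fits sit a little high because absorption is not quite finished just after the peak.

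**The case against.** The strongest reply is that the SAP, read as a whole, already keeps imputed values out. Section 7.1 says *observed*, Table 7 says *measurable*, and 4.1 is introduced as conventions for tables, figures and listings. An LLOQ/2 value is not an observed concentration, and the specific section should govern the general one. This largely stands. A reader might infer that the SAP prescribes a half-life biased by imputation, but the documents do not support that: they leave the choice unstated. They do not close it either. *Observed* is never defined against imputed values, *measurable* qualifies only AUC0-t, and 4.1 also holds derivation rules (baseline, study day), so its opening line does not confine it to display.

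A second reply is that the size rests on invented inputs. That stands too. The large upward shifts need sparse sampling running many half-lives past the peak, and nothing visible shows that this trial has such a schedule. A downward shift is not always an error, as schedule B shows.

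Neither reply touches the one-point minimum, which fails on any reading of 4.1.

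**Conclusion.** The minimum of one post-peak concentration is too low and should be replaced. That conclusion needs no assumption about the data. The LLOQ/2 gap is a missing sentence, not a prescribed bias. If imputed values did enter the fit, t1/2 could roughly double on a sparse schedule (4.1 versus 2.1 d) or fall by about an eighth (4.4 versus 5.05 d), while denser schedules show little or no change in most cases. These figures rest on the assumed profile, schedules and peak/LLOQ ratios, so neither size nor direction can be stated for this trial.

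A reader might also infer a risk to dose escalation. The visible text does not support that: SAP 13.1 bases safety and the MTD on dose-limiting toxicities and adverse events, and no visible rule there uses t1/2. The PK summaries are descriptive. Severity is minor. The plasma/serum mismatch is a wording correction with no analytic effect.

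**What to change.** In SAP 7.1:
- Replace the one-concentration condition with a minimum number of quantifiable terminal concentrations (for example 3) and state whether the peak is in the fit. The documents give no cut-off, so the PK lead should set it.
- Where the minimum is not met, report t1/2, AUC0-inf, CL/F and Vd/F as not estimable, and still report Cmax, Tmax and AUC0-t.
- State that values at or below the LLOQ after the last quantifiable concentration are excluded from Kel and AUC, and that LLOQ/2 is used only for plots and descriptive concentration summaries.

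In SAP 4.1, replace the dataset-wide scope with a reference to 7.1 and align plasma with serum.

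The cost is SAP wording, plus some sparse or low-dose profiles becoming not estimable. On the sparse assumed schedule the quantifiable post-peak counts at peaks of 20 and 50 times the LLOQ are 1 and 2 (true 2 d), 2 and 3 (3 d), and 3 and 4 (5 d). A 3-point minimum therefore fails in 3 of 6 cases if the peak does not count and in 1 of 6 if it does. On the two denser schedules it fails in none.

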## 4.2 ANALYSIS SETS

The following analysis sets are defined for both the periodic safety reviews and the final study analysis. They will consist of all randomized subjects with data available at the time of analysis and will therefore change with each subsequent run.

### 4.2.1 INTENT-TO-TREAT ANALYSIS SET

The intent-to-treat analysis set (ITT) consists of all randomized subjects. Subjects will be included in the treatment group assigned at randomization regardless of the actual treatment received. All efficacy endpoints will be analyzed based on the ITT.

### 4.2.2 FULL ANALYSIS SET

The full analysis set (FAS) consists of all randomized subjects at the time of analysis who received any study drug (PT101 or placebo). Treatment groups will be determined using the actual treatment received, regardless of the randomization treatment assignment. If different from the ITT, efficacy endpoints will also be analyzed based on the FAS.

### 4.2.3 PER PROTOCOL ANALYSIS SET

This study will contain two per protocol analysis sets. The first per protocol analysis set (PP1) will include all subjects in the FAS who were not on concomitant corticosteroids during the treatment period. The second per protocol analysis set (PP2) set will consist of all subjects in the FAS who did not have any major protocol deviations that might impact the efficacy analyses. Exclusion of subjects from the PP will be determined in a final blinded data review meeting that will be held prior to unblinding the randomization list. Reasons for exclusion will be documented for each subject. All exploratory efficacy endpoints will be analyzed based on the PP for the final analysis.

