24. Exposure to advanced therapy within 5 half-lives of the specific therapy of the Day 1 visit or documentation of detectable drug during screening.
25. Subjects receiving concomitant medications for UC (i.e., oral probiotics, aminosalicylates, thiopurines, and/or oral corticosteroids) that have not been administered at stable doses 2 weeks prior to the screening endoscopy or subjects unable or unwilling to maintain stable doses of medications through (b) (4) of the study conduct. Subjects taking oral prednisone or equivalent not greater than 20 mg per day, or budesonide 9 mg per day are eligible.
26. Subjects unable to discontinue topical enemas within 2 weeks prior to endoscopy.
27. Received a live attenuated vaccine $<$ 4 weeks prior to screening or is planning to receive a live attenuated vaccine during the study conduct or up to 12 weeks after the last dose of study drug.

28. Any clinically significant laboratory abnormality, which, in the opinion of the investigator, presents a safety concern to the subject, will prevent the subject from completing the study or will interfere with the interpretation of the study results.
29. Currently enrolled in another investigational device or drug study, or it has been less than 30 days or 5 half-lives (whichever is the longest) since ending another investigational device or drug study, or receiving another investigational agent.
30. Is pregnant or nursing or is planning to become pregnant during the study.
31. Any uncontrolled or clinically significant concurrent systemic disease other than UC.
32. Any condition or disease that, in the opinion of the Investigator, would pose a risk to subject safety or interfere with study evaluation, procedures or completion.
33. Has a median QTc interval >450 ms on screening triplicate ECG, has a history of risk factors for Torsades de Pointes (e.g., heart failure/cardiomyopathy or family history of long QT syndrome), has uncorrected hypokalemia, or is taking concomitant medications that prolong the QT/QTc interval.

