5.2.3 Allowed Concomitant Therapy

Concomitant medications for UC (i.e., oral probiotics, aminosalicylates, thiopurines, and/or oral corticosteroids) must be at stable doses 2 weeks prior to the screening endoscopy; a subject must be willing to maintain stable doses of these medications ^{CCI} [REDACTED] Oral prednisone or equivalent at doses ≤ 20 mg per day or budesonide ≤ 9 mg are permitted.

Low-dose aspirin for cardioprotection and/or temporary use of NSAID for minor ailments (other than for reasons related to the subject's underlying UC) may be used without prior consultation with the Medical Monitor.

The use of opioids related to the study procedure is allowed. Opioids used PRN should be assessed by the investigator on a case-by-case basis and upon consultation with the Medical Monitor.

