9.3.2.3 Per Protocol Analysis Set

The PP analysis set will consist of all subjects in the FAS who did not have any major protocol violations that might impact the efficacy analyses.

Exclusion of subjects from the PP analysis set will be determined in a final blinded data review meeting that will be held prior to unblinding the randomization list. Reasons for exclusion will be documented for each subject.

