### 5.5.2 CONCOMITANT MEDICATION

Any medication with a start date prior to or on the first dosing date and continuing to take after the first dosing date or started after the first dosing date will be considered concomitant medications. If the start date of a medication is incomplete or missing, the medication will be assumed to be concomitant medication, unless the incomplete start date (month and/or year) or the stop date (complete or incomplete) clearly indicate that the medication stopped prior to first dosing date. Medication with completely missing start and stop dates will be included in the concomitant medication summary. Concomitant medications will be summarized for each study phase and listed. Additionally, a summary and listing of subjects who tapered off corticosteroids will be provided.

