## **6 EFFICACY ANALYSES**

Efficacy analyses will be primarily based on the ITT, and the FAS, if different. The efficacy analyses will also be performed on the PP for confirmatory purposes.

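### PP1 is labelled per-protocol but is selected on corticosteroid use during treatment: it drops compliant users of permitted steroids and subjects who start steroids after randomisation

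*SAP*

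**What the plan says.** SAP Section 4.2.3 defines two per-protocol sets. PP1 "will include all subjects in the FAS who were not on concomitant corticosteroids during the treatment period". PP2 is the conventional set: "subjects in the FAS who did not have any major protocol deviations that might impact the efficacy analyses". The protocol has one per-protocol set (Section 9.3.2.3), "all subjects in the FAS who did not have any major protocol violations that might impact the efficacy analyses", which PP2 carries forward.

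The protocol allows oral corticosteroids. In Section 4.2, criterion 25: "Subjects taking oral prednisone or equivalent not greater than 20 mg per day, or budesonide 9 mg per day are eligible". In Section 5.2.3: "Oral prednisone or equivalent at doses ≤ 20 mg per day or budesonide ≤ 9 mg are permitted", under the condition that "Concomitant medications for UC (i.e., oral probiotics, aminosalicylates, thiopurines, and/or oral corticosteroids) must be at stable doses". SAP Section 5.5.2 counts as concomitant "Any medication with a start date prior to or on the first dosing date and continuing to take after the first dosing date", as well as anything started later.

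On use of the sets, SAP Section 6 makes ITT (and FAS, if different) primary for efficacy and adds: "The efficacy analyses will also be performed on the PP for confirmatory purposes". Section 4.2.3 plans all exploratory efficacy endpoints on the PP at the final analysis. Section 6.2.5.1 repeats the binary analyses, with non-responder imputation (NRI), in the PP as a robustness check. None of these three places says whether PP1 or PP2 is meant.

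**The concern.** A per-protocol set should separate subjects who followed the protocol from those who did not. PP1 sorts on something else, and part of what it sorts on happens after randomisation. A subject whose UC worsens and who is given a steroid is, for a response endpoint, most naturally a failure. In PP1 that subject leaves both numerator and denominator. If steroid starts differ by arm, the arms of PP1 are no longer comparable, and a robustness analysis meant to reassure the reader carries a selection effect of its own. Deciding exclusions at a blinded meeting does not cure this, because the selecting event can itself be a consequence of treatment.

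**Working it through.** The plan states no figure on this point, so there is none to reproduce. The check is a comparison of definitions, followed by an illustration.

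**Step 1. Who is in which set.** Inputs: SAP 4.2.3, 5.5.2, 6.2.4.1 and 6.2.5.1; Protocol 4.2, 5.2.2, 5.2.3 and 5.2.3.1.

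| Subject | PP1 | PP2 | ITT, binary endpoints |
|---|---|---|---|
| Compliant, on a permitted stable oral steroid since before Day 1 | out | in | observed outcome |
| Never on steroids, major deviation affecting efficacy | in | out | observed outcome |
| Starts a steroid after Day 1, stays in the study and is assessed | out | depends on deviation classification | observed outcome |
| Starts a steroid after Day 1, leaves the study before the timepoint | out | depends on deviation classification | non-responder |

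The first two rows show that PP1 misclassifies adherence in both directions. The last two show the post-randomisation selection. NRI (SAP 6.2.4.1) is triggered by leaving the study or by lacking an adequate assessment. Applied within the PP, it cannot reach a subject who has already been removed.

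NRI does not name a steroid start or increase in any set. Protocol 5.2.3.1 requires study discontinuation when the steroid dose goes above the screening dose, but it stands in the tapering section. Protocol 5.2.2 stops study drug, not study participation, when a rectal steroid is started.

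**Step 2. How much PP1 could shrink.** Inputs: 8 PT101 and 2 placebo per cohort (Protocol 9.1), so 24 and 6 over the three planned cohorts. The share on steroids, s, is not given; assume 20% to 50%, equal in both arms and independent between subjects.

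- Expected size is n(1 − s). For 24 + 6 this gives 19.2 + 4.8 at s = 0.2 and 12.0 + 3.0 at s = 0.5.
- The chance that a cohort keeps no placebo subject is s²: 0.2² = 4% and 0.5² = 25%.
- The chance that at least one of three cohorts keeps none is 1 − (1 − s²)³: 1 − 0.96³ = 11.5% and 1 − 0.75³ = 57.8%.

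**Step 3. What dropping starters can do to a response rate.** Among subjects not on steroids at Day 1, let p be the response rate with starters counted as non-responders, and let i be the share who start. If all starters are failures, the PP1 rate is p/(1 − i). Assume no drug effect, so p is the same in both arms. The start rates are assumptions.

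| p | i, PT101 | i, placebo | PP1 rate, PT101 | PP1 rate, placebo | Difference, points |
|---|---|---|---|---|---|
| 30% | 5% | 5% | 31.6% | 31.6% | 0 |
| 30% | 5% | 20% | 31.6% | 37.5% | −5.9 |
| 30% | 5% | 30% | 31.6% | 42.9% | −11.3 |
| 20% | 5% | 20% | 21.1% | 25.0% | −3.9 |
| 20% | 5% | 30% | 21.1% | 28.6% | −7.5 |

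Keeping starters as non-responders gives a difference of 0 in every row. Dropping them raises both rates, and creates a difference only when start rates differ between arms.

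**The case against.** Four arguments can be made for leaving PP1 alone.

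- *It is secondary.* Because SAP Section 6 calls the PP analyses confirmatory, a reader might infer that efficacy rests on PP1. The documents do not support that. ITT/FAS is primary, all efficacy endpoints are exploratory (Protocol 2.2.3), the analyses are described as descriptive (Protocol 9.3.4), and SAP 6.2.5.1 treats the PP as a robustness check. This stands and limits the size of the point.
- *It is allowed.* Since SAP Section 14 does not mention PP1, a reader might infer an undeclared departure from the protocol. Protocol 9.3.2.4 lets the SAP define additional sets, so this inference fails.
- *Every per-protocol set selects after randomisation.* This is true. A steroid starter might also be classed a major deviator and leave PP2; the classification is in a deviation plan that is not part of these documents. But PP2 at least selects on deviations, which is its stated purpose. PP1 removes permitted users whatever their adherence.
- *Steroid use is handled elsewhere.* Oral corticosteroid use is a candidate covariate in SAP 6.2.3, and a steroid-free look is a reasonable supportive question. Both are true, but neither requires defining the group by what happened after Day 1.

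**Conclusion.** The point holds as one of definition and labelling in a supportive analysis. PP1 is a steroid-free subset, not a per-protocol set, and part of its membership depends on a post-randomisation event that can reflect treatment failure. The main efficacy results do not depend on it.

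A reader might infer that PP1 would flatter PT101. The documents do not support that. Direction and size depend on steroid-start rates by arm, which are not given. If placebo subjects start more often, PP1 works against PT101, by about 4 to 11 points under the assumptions shown. If starts are equal and all starters are failures, both rates rise and, with no drug effect, the difference stays at zero. Step 3 illustrates the mechanism; it is not an estimate for this trial.

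**What to change.** Change the SAP wording as follows, before the final database lock:

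1. Replace PP1 with a subset of subjects with no systemic corticosteroid use at baseline, and do not call it per-protocol. Baseline use is already recorded as yes/no (SAP 5.3). State whether oral budesonide counts as systemic.
2. Within that subset, keep subjects who start steroids for UC after Day 1 and count them as non-responders for the binary endpoints. Apply the same analysis rule in ITT and FAS, where SAP 6.2.4.1 is silent on steroid starts.
3. Keep PP2 as the only per-protocol set, and state that the PP in SAP 4.2.3, 6 and 6.2.5.1 means PP2.

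The baseline flag needs no new data. Whether a given start was for UC is a judgement that can be settled at the blinded data review already planned in SAP 4.2.3. The downside is that the steroid-free subset will contain some subjects who later took steroids, so a table footnote should give their number by arm.
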